11.3. Analysis of Outcome Measures

Summary statistics, including means, medians, and variances, will be calculated at each time point and for each type of data (e.g. parameters derived from index AF procedure and follow-up visits).

If patients withdraw from the study we will analyse data already collected, unless the patients request otherwise.

12. DATA MANAGEMENT

12.1. Access to Data

Direct access will be granted to authorised representatives from the Sponsor or host institution for monitoring and/or audit of the study to ensure compliance with regulations.

12.2. Data Recording and Record Keeping

- The study staff will ensure that the participants' anonymity is maintained.
- NHS code of confidentiality will be followed.
- All electronic records will be stored on a NHS server within password-protected user accounts.
- Personal data will be anonymised with the use of a study participant number. The study number will be correlated with personal data about the patient in one electronic file, which will be individually password protected and secured as above.
- Paper records will be stored in a locked filing cabinet to which only the research team have access.
- The study will comply with the Data Protection Act which requires data to be anonymised as soon as it is practical to do so.
- Data analysis will be performed by [name] and [name] in the JR hospital. No further data transfer will be performed.
- After the end of the trial period, participant's personal data will be stored and accessible for 5 years.
- Similarly, remaining patient data, labelled only with study participant number, will be kept for a further period of up to 5 years to allow for full analysis and results publication, as per Trust Policy, before being deleted.

13. ETHICAL AND REGULATORY CONSIDERATIONS

13.1. Declaration of Helsinki

The Investigator will ensure that this study is conducted in accordance with the principles of the Declaration of Helsinki.

13.2. Guidelines for Good Clinical Practice

The Investigator will ensure that this study is conducted in accordance with relevant regulations and with Good Clinical Practice.

13.3. Approvals

The protocol, informed consent form, participant information sheet and any proposed advertising material will be submitted to an appropriate Research Ethics Committee (REC), and host institution(s) for written approval.

The Investigator will submit and, where necessary, obtain approval from the above parties for all substantial amendments to the original approved documents.

13.4. Reporting

The CI shall submit once a year throughout the study, or on request, an Annual Progress report to the REC Committee, host organisation and Sponsor. In addition, an End of Study notification and final report will be submitted to the same parties.

13.5. Participant Confidentiality

The study staff will ensure that the participants' anonymity is maintained. The participants will be identified only by initials and a participants ID number on the CRF and any electronic database. All documents will be stored securely and only accessible by study staff and authorised personnel. The study will comply with the Data Protection Act, which requires data to be anonymised as soon as it is practical to do so.

13.6. Expenses and Benefits

Reasonable travel expenses for any visits additional to normal care will be reimbursed on production of receipts, or a mileage allowance provided as appropriate.

We intend that the majority of study visits will be performed at the time of routine clinical visits to hospital so would not expect that patients will have to make many extra visits to hospital.

Light refreshments will also be available.

14. FINANCE AND INSURANCE

14.1. Funding

The study will be supported by the Cardiac Rhythm Management Unit, which research funds will be used to cover additional expenses apart from standard medical care.

14.2. Insurance

NHS bodies are legally liable for the negligent acts and omissions of their employees. If you are harmed whilst taking part in a clinical research study as a result of negligence on the part of a member of the study team this liability cover would apply.

Non-negligent harm is not covered by the NHS indemnity scheme. The Oxford University NHS Trust, therefore, cannot agree in advance to pay compensation in these circumstances.

In exceptional circumstances an ex-gratia payment may be offered.

15. PUBLICATION POLICY

The Investigators will be involved in reviewing drafts of the manuscripts, abstracts, press releases and any other publications arising from the study. Authorship will be determined in accordance with the ICMJE guidelines and other contributors will be acknowledged.

[figure not shown]

APPENDIX A: STUDY FLOW CHART

APPENDIX B: SCHEDULE OF TIMING OF STUDY APPOINTMENTS AND STUDY PROCEDURES

	Recruit-ment	Baseline visit	Study intervention	Pre-discharge review	Telephone f-up 1	Arrhythmia Clinic visit	Telephone f-up 2
Time since AF ablation	≥ 6 wks	- 1-2 wks	0	+ 1 d	+ 3 mts	3-4 mts	+ 6 mts
Study procedures							
Eligibility assessment	X	X					
Patient's information	X						
Informed consent		X					
Randomisation		X					
Demographics		X					
Medical history		X		X	X	X	X
ECG		X	X	X		X	
AF ablation			X				
Symptom diary instruction				X			
Symptom diary collection					X	X	X

d = day; f-up = follow-up; mts = months; wks = weeks.

17. APPENDIX C: AMENDMENT HISTORY

Amendment No.	Protocol Version No.	Date issued	Author(s) of changes	Details of Changes made
1	1.1	11/11/2015	Dr [name]/ Dr [name]	
Method of randomization clarified in detail (paragraph 8.2.3, page 14)
 
As requested by Ethic Committee, period of time during which the patients' personal data will be stored and accessed after the study prolonged to 5 years (paragraph 12.2, page 2)

2	1.2	10/03/2016	Dr [name]/Dr [name]	
On the basis of observations during the first 10 research cases, study intervention protocol modified as follow:
 
 - FTI removed from the target parameters for termination of RF delivery on the LA posterior wall; - maximal duration cut-off of 60 sec added for RF delivery on the LA posterior wall.

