1. SYNOPSIS

Study Title	Radiofrequency Power, Lesion Size Index and Oesophageal Temperature alerts during Atrial Fibrillation ablation: a pilot study	
Internal ref. no. / short title	PiLOT-AF study	
Study Design	Prospective, randomized, single centre observational clinical investigation	
Study Participants	Patients admitted for elective radiofrequency (RF) ablation for paroxysmal or persistent atrial fibrillation (AF)	
Planned Sample Size	80 patients (pilot study)	
Planned Follow-up duration	6 months	
Planned Study Period	15 months	
	Objectives	Outcome Measures
Primary	Assessment of the risk of oesophageal damage associated with radiofrequency (RF) ablation on the left atrial (LA) posterior wall when using different power settings	Luminal oesophageal temperature rises > 39°C during RF application on the LA posterior wall as recorded by an oesophageal temperature probe
Secondary	
Comparison of oesophageal complications with the different RF settings on LA posterior wall
 
Comparison of acute and short-term procedure success using different RF settings on LA posterior wall as marker of lesion transmural and durability
	
Symptoms of oesophageal injury during 6 months follow-up
 
Rate of first-pass pulmonary vein isolation (PVI), rate of acute pulmonary vein reconnection (PVR), total procedure time and RF time of the index ablation procedure
 
AF-free survival during 6 months follow-up

Tertiary	Comparison of rate of procedural complications using the different RF settings	pericardial effusion, TIA/stroke, phrenic nerve injury, pulmonary vein stenosis, open-heart surgery, death

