- *LA ablation strategy and technique.* The PVs will be encircled in pairs to isolation using an irrigated-tip ablation catheter TactiCath Quartz (SJ Medical, St Paul, MN, USA) via an Agilis deflectable sheath. A point-by-point ablation technique will be used, with a minimum CF of 10 g and a target CF of 20 g for each RF lesion. As current practice, the circumferential ablation line around the PV pairs will be predefined on the electroanatomical LA map, at 1-2 cm from PV ostia with individual adjustments in order to avoid RF delivery in close proximity of the oesophageal probe.

- *RF settings on the LA anterior wall, roof and floor.* As current practice in our centre, an RF power of 40 W will be used on LA anterior wall, roof and floor. The RF application time will be dictated by the achievement of the target FTI and LSI (FTI \geq 400 gs; LSI \geq 6 on LA anterior wall and LSI \geq 5.5 on LA roof and floor).

- *RF settings on the LA posterior wall.* Different RF settings will be used during RF ablation on LA posterior wall, according to randomization group:

- ✓ *Group 1:* 20 W RF power, with target LSI = 4;
- ✓ *Group 2:* 40 W RF power, with target LSI = 4;
- ✓ *Group 3:* 20 W RF power, with and target LSI = 5;
- ✓ *Group 4:* 40 W RF power, with target LSI = 5.

Regardless of the LSI achieved, RF delivery on the LA posterior wall will be promptly terminated in case of any oesophageal temperature rise \geq 39°C or after 60 seconds of continuous RF delivery. The ablation catheter will be then moved to a contiguous lower or higher site on the predefined circumferential ablation line.

- *PVI confirmation.* Disappearance of PV potentials or dissociated PV potentials in the vein and inability to capture the LA during PV pacing will confirm bidirectional block across the PV circumferential ablation line and PVI.

- *Waiting time.* After a waiting time of 30 min, the PVs will be rechecked in order to confirm the persistence of PVI.

- *Acute PVR.* In case of acute PVR, additional RF ablation will be performed in correspondence of breakthrough signals. The same RF settings of the first PV encirclement will be used.

- *Procedure completion.* The procedure will be terminated after achievement of electrical isolation of all PVs. A trans-thoracic echocardiogram will be performed at the end of the procedure to rule out the presence of pericardial effusion. Protamine will be administered to reverse heparin.

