11. STATISTICS AND ANALYSIS

11.1. The Number of Participants

The PiLOT-AF study aims to give some insights about the relation among RF power, LSI and incidence of oesophageal temperature alerts during AF ablation on the LA posterior wall. In view of the absence of data on this topic, it has been designed as pilot study for power analysis and sample size calculation of a further main study.

As suggested before for pilot studies (38), we aim to a final sample size of 12 patients with primary outcome data per each treatment group. We know from previous studies that oesophageal temperature alerts occur in 55-75% of AF ablations. Therefore, if taking into account also participants who do not experience oesophageal temperature alerts during AF ablation, we plan to recruit a total of 80 patients in order to achieve primary outcome data in 12 patients per group.

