11.2. Description of Statistical Methods

Comparison of primary, secondary and tertiary outcome measures among different treatment groups will be performed at each time point using appropriate statistical testing. In particular, ANOVA tests will be used to compare numerical variables and chi-square tests will be used to compare categorical values.

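### At least the first 10 of 80 patients were ablated before the posterior-wall stopping rule changed, and the analysis plan makes no allowance for this

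*Combined protocol and SAP*

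**What the plan says.** Appendix C lists amendment 2 (protocol version 1.2, issued 10/03/2016). It begins "On the basis of observations during the first 10 research cases, study intervention protocol modified as follow" and names two changes: "FTI removed from the target parameters for termination of RF delivery on the LA posterior wall" and "maximal duration cut-off of 60 sec added for RF delivery on the LA posterior wall". Section 9 carries the rule now in force: posterior-wall delivery stops, whatever LSI has been reached, on an oesophageal temperature rise "or after 60 seconds of continuous RF delivery".

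On analysis, section 11.2 says "Comparison of primary, secondary and tertiary outcome measures among different treatment groups will be performed at each time point", with ANOVA for numerical and chi-square for categorical outcomes. Section 11.1 says "we plan to recruit a total of 80 patients in order to achieve primary outcome data in 12 patients per group". Section 8.2.3 lays out the allocation of all 80 patients as four blocks of 20. Section 8.7 has the only rule that both excludes and replaces a patient, and it covers withdrawal before the intervention. None of these sections mentions protocol version.

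**The concern.** The point is not that the amendment log differs from the current text. The log establishes a fact about enrolled patients: some were treated under a stopping rule that the protocol no longer contains. Section 11 does not say how their data are used. Applying the sections above as written puts them in the same unadjusted comparison as everyone else.

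This matters because both changes act on how long each application lasts. Section 3.4 asks whether higher power for shorter times is better than lower power for longer times. Section 3.3 describes oesophageal injury as a time-dependent effect of heat conduction and says that lower power generally means longer applications. A time limit can therefore take effect more often in the 20 W arms than in the 40 W arms. RF ablation time is itself a secondary outcome (section 4).

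At stake is what the alert rate, first-pass isolation rate and RF time describe. Section 11.1 says the pilot exists to supply figures for sizing a main study. Planning figures averaged over two stopping rules do not describe exactly the intervention now defined in section 9.

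**Working it through.** **Inputs.** Planned total 80, four arms, target of 12 patients with primary outcome data per arm, and the statement that "oesophageal temperature alerts occur in 55-75% of AF ablations" (all section 11.1); patients treated before the change, at least 10 (Appendix C); block sizes (section 8.2.3).

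**1. The plan's own sample size.** Number per arm = 12 / alert rate, rounded up, times 4.
- 55%: 12/0.55 = 21.8, so 22 per arm, total 88
- 60%: 12/0.60 = 20 per arm, total 80
- 65%: 12/0.65 = 18.5, so 19 per arm, total 76
- 75%: 12/0.75 = 16 per arm, total 64

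The stated 80 is reproduced at 60%. The protocol does not say which rate was used.

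**2. Share affected.** 10/80 = 12.5%, on average 10/4 = 2.5 of the 20 patients in each arm. This is a minimum. Appendix C gives an issue date but not the date the new rule took effect, and anyone ablated between the tenth case and that date also belongs to the earlier group. The version 1.2 set therefore has at most 70 patients, or 17.5 per arm.

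**3. Spread of the first ten over the arms.** This assumes that the first ten ablated are the first ten randomised.

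*Blocks of 20, five per arm.* There are C(20,10) = 184,756 equally likely ways to choose which ten of the 20 allocations come first.
- Split 3,3,2,2: 6 × 10⁴ = 60,000 ways (largest gap 1)
- Split 4,2,2,2: 4 × 5 × 10³ = 20,000 ways (gap 2)
- Split 3,3,3,1: 4 × 5 × 10³ = 20,000 ways (gap 2)
- All other splits have a gap of 3 or more: 1 − 100,000/184,756 = 0.459

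*Blocks of four.* Two full blocks give two per arm, and the remaining two patients go to different arms. Each arm has 2 or 3, and a gap of 3 cannot occur.

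The chance of a gap of three or more is thus 46% or 0%, depending on which sentence of section 8.2.3 was followed.

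**4. Possible effect on an arm's alert rate.** The documents give no figure. Assume that the earlier rule shifts a patient's alert probability by 10 to 50 points. With k early patients among 20, the arm's rate shifts by (k/20) × shift.
- k = 2 or 3: from 2/20 × 10 = 1 point to 3/20 × 50 = 7.5 points
- k = 5 (the most possible within a block of 20): from 2.5 to 12.5 points

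The sign is not known.

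**5. Cost of restricting to version 1.2.** Standard errors grow by a factor of sqrt(80/70) = 1.07, or more if fewer than 70 remain. Expected alert patients per arm among 17.5, compared with 20:
- 55%: 9.6 (compared with 11)
- 60%: 10.5 (12)
- 65%: 11.4 (13)
- 75%: 13.1 (15)

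The target of 12 is met on average only if the alert rate is at least 12/17.5 = 68.6%.

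**The case against.** The strongest reply is that this is a pilot with no stated alpha, power or effect size, and that refining a procedure early is an ordinary use of a pilot. The amendment changes neither randomised factor, and as logged it applies to all arms alike. Section 3.3 also reports that, in the centre's experience, alerts tend to come before LSI 5 at any power. Where an alert ends the application first, neither the removed target nor the new limit has any effect. All of this stands, and it limits the size of the problem. It does not supply a rule for analysing the earlier patients.

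A reader might infer more than the documents support:
- **That pooling is the stated plan.** No section says so. It follows from the absence of any other rule.
- **That the split is exactly 10 and 70.** Ten is a minimum and 70 a maximum.
- **That the effect is diluted**, for example a true 20-point difference appearing as 20 × 70/80 = 17.5. This requires no contrast at all between settings among the early patients. If the time limit mainly shortens 20 W applications, patients without it could show a larger contrast between powers, and pooling would exaggerate the difference.
- **That the earlier FTI target forced a minimum application time whatever the LSI.** The superseded text is not available. Neither the posterior-wall FTI value nor the way it combined with the LSI target is known.

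**Conclusion.** The point holds as a gap in the analysis plan. At least 12.5% of the planned patients were treated under a stopping rule that has since changed, and the analysis as written averages over both rules. What is affected is the quantity being estimated, and with it the planning figures. It would be too strong to say that the arm comparison is invalid or that the randomised settings were altered: power and target LSI are the same before and after, and allocation remained random.

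The size is likely to be modest but cannot be fixed from the documents. The shift of 1 to 7.5 points for an arm with two or three early patients rests on an assumed effect of 10 to 50 points per patient. The 46% chance of an uneven spread rests on blocks of 20 and on ablation following randomisation order. The possibility of unequal action on the 20 W and 40 W arms rests on section 3.3's own account of power and duration. This is a worthwhile, inexpensive improvement. No view is taken on which stopping rule is preferable.

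**What to change.** Add to section 11.2:
- Record the protocol version in force at each ablation.
- Report the number of patients per arm under each version.
- Keep the all-patient comparison by arm.
- Prespecify a sensitivity analysis of the primary and procedural outcomes (alerts, first-pass isolation, acute reconnection, procedure time, RF time), either restricted to version 1.2 patients or stratified by version. The two do different work: restriction describes the rule now in section 9, while stratification mainly removes any uneven spread of early patients over the arms.
- Report main-study planning figures for all patients and for version 1.2 patients side by side. Relying on the version 1.2 set alone is debatable given its size.

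Section 8.2.3 should also state which block size was used, since that determines how uneven the early group could be.

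The cost is one extra analysis. In the version 1.2 set, standard errors are at least about 7% larger, and the target of 12 alert patients per arm is met on average only if the alert rate is about 69% or higher, within a stated range of 55–75%. Because the all-patient analysis is kept, no information is lost.
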